#### 7.7 Measures to Reduce and Avoid Bias

Training for investigators: Before the clinical trial, the investigators are trained by the protocol and are told how to use the experimental product, so that investigators can familiarize themselves with the investigational product and find new product-related information during the clinical trial.

Monitoring for the trial: The monitor appointed by the sponsor will regularly monitor the trial hospital on site, to guarantee that the study protocol is strictly abided by. The monitor will also check the original data to ensure their consistency with those in the case report form (CRF).

Additionally, if the patients' baseline information (age, gender, lesion location) between two groups aren't balanced, we will use the propensity score method (PSM) to match this information.

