### 11.2 Justification for Cases

The null hypothesis: the Successful localization probability of the novel localization device isn't higher compared with hookwire.

The alternative hypothesis: the Successful localization probability of the novel localization is higher compared with hookwire.

 $\alpha$  refers to type I error, while  $\beta$  refers to type II error. Here we consider  $\alpha$  as 0.05, and power(1- $\beta$ ) as 80%. According to some reference and our previous study, we consider the Successful localization probability of hookwire as 89% and the Successful localization probability of the novel localization device as 97%, with

one side and the ratio of 2 between control group and intervention group.

We use PASS 11 with Fisher's exact test to calculate the sample size, getting control group with 116 and intervention group with 232. Taking possible 15% drop-out into account, every group will be enrolled 136 patients in the control group and 273 in the intervention group at least. Here, if we can enroll more patients during enrollment time, the patients could be included in our study. This clinical trial can be deemed as successful if the successful localization probability of the novel localization and hookwire is different, addition the successful localization probability of the novel localization has statistic significantly higher than the successful localization probability of hookwire (p < 0.05).

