# 11.4 Significance Level and Power of the Trial

Significance level: 0.05; power: 0.8.

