### 11.7 Interim Analysis and Sensitivity Analysis

This study has no interim analysis and sensitivity analysis.

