# 11.8 Deviation Reporting Procedures

The original statistical plan should be strictly complied with. Other statistical methods, which are not specified in the protocol, can be used only after having been reviewed and approved by the ethics committee.

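### Section 7.7 commits a randomised trial to propensity-score matching if baseline looks unbalanced, with no stated role beside the primary comparison and no allowance in the sample size for patients it drops

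*Protocol*

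**What the plan says.** Section 7.7 names three baseline variables (age, gender, lesion location) and says that if the groups are not balanced on them, "we will use the propensity score method (PSM) to match this information". It does not say what the matched comparison is for.

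The rest of the plan is written for an unmatched comparison:

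- Section 11.1 defines three analysis sets and assigns the primary and secondary endpoints to the Safety Analysis Set. A matched subset is none of the three.
- Section 11.2 gives the sizing: "We use PASS 11 with Fisher's exact test to calculate the sample size, getting control group with 116 and intervention group with 232". The only allowance on top is 15% for drop-out.
- Section 11.3.1 plans a chi-square test, or Fisher's exact test when an expected frequency is below 5, with no matching.
- Section 11.7: "This study has no interim analysis and sensitivity analysis".
- Section 11.8: "The original statistical plan should be strictly complied with".

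**The concern.** Under randomisation, a difference between the arms in age, gender or lesion location arises by chance. The type I error rate of the randomised test is calculated over all such chance allocations, so no repair is needed for the test to be valid. Matching adds a step that depends on the observed baseline data, changes the set of patients analysed and removes randomised patients from the comparison.

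The more serious problem is its unstated role. Section 11.2 ties success of the trial to p < 0.05 on the primary endpoint. If section 7.7 is triggered, the protocol supports both an unmatched comparison (section 11) and a matched one (section 7.7), and does not say which decides. Section 11.7 leaves no room to treat the matched result as a declared sensitivity analysis. In an open-label trial, which result counts should be fixed in advance. Power is also at stake, because the trial was sized for all evaluable patients in both arms.

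**Working it through.** **Inputs from the protocol**

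- Section 11.4: "Significance level: 0.05; power: 0.8".
- Section 11.2, success rates: "we consider the Successful localization probability of hookwire as 89% and the Successful localization probability of the novel localization device as 97" (both per cent).
- Section 11.2, sidedness and ratio: "one side and the ratio of 2 between control group and intervention group". The counts of 116 and 232 show that the novel-device arm is the larger.
- Section 11.2, enrolment: "every group will be enrolled 136 patients in the control group and 273 in the intervention group at least", 409 in total.

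**Assumptions, not in the protocol:** the matching ratio (1:1 and 1:2 are both examined), matching without replacement, and the threshold for calling the groups unbalanced.

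**Step 1. The plan's own figure.** Exact power of Fisher's test is the sum, over all pairs of success counts, of Bin(x; n_control, 0.89) × Bin(y; n_novel, 0.97), taken over the pairs that Fisher's test declares significant at 0.05. At 1:2 allocation:

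- Two-sided: the smallest size reaching 80% is 113/226, and 116/232 gives 81.3%. This is close to the stated size.
- One-sided, as the text states: the smallest size is 102/204, and 116/232 gives 84.4%.
- Drop-out: 116/0.85 = 136.5 (stated 136) and 232/0.85 = 272.9 (stated 273).

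The stated size is therefore adequate for the unmatched comparison on either sidedness. Both are carried forward.

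**Step 2. What matching can do at 1:2 allocation.** If all 116 controls are matched 1:2 without replacement, the matched set is the same 116 + 232 = 348 patients, and the arm-level balance is unchanged. Balance can improve only if some patients are left out.

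**Step 3. Patients lost under 1:1 matching, every control matched.**

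- Evaluable: 348 − (116 + 116) = 116 dropped; 116/348 = 33.3%.
- Enrolled, no drop-out: 409 − (136 + 136) = 137 dropped; 137/409 = 33.5%.

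**Step 4. Power at 89% v 97%, level 0.05.**

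| Control/novel | Fisher 1-sided | Fisher 2-sided | Chi-square 1-sided | Chi-square 2-sided |
|---|---|---|---|---|
| 116/232, unmatched | 84.4% | 81.3% | 90.0% | 84.3% |
| 116/116, 1:1 | 71.2% | 57.9% | 81.1% | 70.3% |
| 136/136, 1:1, no drop-out | 78.2% | 67.5% | 86.2% | 76.2% |
| 104/208, 1:2, 90% of sets kept | 80.8% | 76.8% | not run | not run |
| 99/198, 1:2, 85% of sets kept | 78.7% | 74.7% | not run | not run |

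**Step 5. Which test section 11.3.1 would choose.** At 116/116 the expected failures are 116 × 0.11 + 116 × 0.03 = 16.24, or 8.12 per arm under the null. That is above 5, so at the planning rates section 11.3.1 would normally select chi-square, although the trial was sized on Fisher's test.

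**Step 6. How often chance would trigger matching.** If imbalance meant p < 0.05 on any of three independent variables, the probability is 1 − 0.95³ = 0.143, about 14% of correctly randomised trials.

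**The case against.** Several points on the other side stand.

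- **The ratio is not given.** A reader might infer that the plan discards a third of patients and falls below 80% power. The protocol does not support that as a fact. Both statements need 1:1 matching, and the power statement also depends on the test and its sidedness: one-sided chi-square at 116/116 keeps 81.1%, and 1:2 matching that keeps 90% of sets keeps 80.8% one-sided Fisher power.
- **The loss is conditional.** With the assumed 14.3% trigger and 1:1 matching, and treating power as unrelated to the trigger, average Fisher power is 0.857 × 84.4% + 0.143 × 71.2% = 82.5% one-sided, and 0.857 × 81.3% + 0.143 × 57.9% = 78.0% two-sided.
- **Replacement is an inference.** A reader might conclude that matching takes over as the primary analysis. Section 7.7 does not say so. The silence is the defect.
- **Outcome knowledge is not shown.** A reader might suppose that the match would be chosen with results in view. Section 12.1.3 requires data review before lock to meet the standard of blind review. It does not fix when or how matching is decided, but a flat statement that outcomes would be known is not supported.
- **Randomisation is not undone.** The three variables precede treatment. Matching on them alone, without regard to outcome, leaves assignment random given those variables. The cost is efficiency and a changed target population.
- **Section 11.8 is not contradicted.** It restricts methods that the protocol does not specify, and matching is specified in section 7.7.
- **Caliper, ratio and threshold** may properly be left to a statistical analysis plan, so their absence is not the point.

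The aim of section 7.7 is also legitimate: a chance imbalance in a prognostic variable can cloud one trial's estimate. Covariate adjustment serves that aim without dropping patients. None of these points gives the matched result a role or reconciles section 7.7 with the analysis set, test and sizing in section 11.

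**Conclusion.** The point holds as a flaw in a stated rule. The protocol commits to matching on the basis of observed baseline balance, gives the matched result no place beside the primary comparison, rules out sensitivity analyses, and sizes the trial with no allowance for matching losses. At 1:2 allocation, matching without replacement can help balance only by dropping patients.

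The size of the loss is conditional. Under 1:1 matching of all 116 controls it is one third of evaluable patients, with Fisher power falling by about 13 percentage points one-sided (84.4% to 71.2%) or 23 two-sided (81.3% to 57.9%). Under 1:2 matching it may be small. The figure of about 14% for a chance trigger rests on an assumed p < 0.05 rule and independent variables. The need to change the rule does not depend on any of these assumptions.

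**What to change.** 1. Delete the propensity-score sentence in section 7.7.
2. State in section 11 that the primary comparison uses all patients in the planned analysis set, whatever the baseline balance.
3. Prespecify one supportive covariate-adjusted analysis of those same patients, with age, gender and lesion location as covariates. About 20 failures are expected at the planning rates (116 × 0.11 + 232 × 0.03 = 19.7), so the method should be suited to few events. The choice of model can be left to the trial statistician, provided it is fixed before the data are seen.
4. Amend section 11.7 so that this supportive analysis is permitted.

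The cost is protocol wording and one extra model. No patients are added, and section 7.7 already treats the three variables as baseline information that will be available.

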#### 7.8 Standards and Procedures for Discontinuing Trial/Treatment

- Trial discontinuation:
- (1) A huge error of the clinical verification protocol is found during the trial, and the product effectiveness can hardly be evaluated;
- (2) The sponsor or CFDA requires to terminate the trial.
- Treatment discontinuation:
- (1) Withdrawal due to the subject's reason:
  - ◆ The subject does not comply with the verification plan;
  - ◆ Other reason of the subject.
- (2) Withdrawal due to medical reasons:
  - ◆ Poor protocol compliance;
  - ◆ Serious adverse events (SAEs);
  - ◆ Serious complication.

#### • Procedure:

If the trial is discontinued or suspended for any reason, the Principal Investigator (PI)/Clinical Investigation Site should timely notify relevant subjects, fully protect their rights and interests, and ensure that they can receive proper treatment and follow-up. Meanwhile, the PI/Clinical Investigation Site should notify the superior department in charge of medical treatment and public health in accordance with relevant laws,

regulations and management procedures. In addition,

- (1) If the PI discontinues or suspends this trial without reaching any agreement with the sponsor in advance, the PI should immediately notify the administrative department for the clinical trial of medical devices in the Clinical Investigation Site, and timely provide a detailed written explanation for discontinuation or suspension to the sponsor and the medical ethics committee.
- (2) If the sponsor discontinues or suspends this trial, the PI should immediately notify the administrative department for clinical trial of medical devices in the Clinical Investigation Site, and timely provide detailed written explanation for discontinuation or suspension to the medical ethics committee.
- (3) If the medical ethics committee discontinues or suspends its approval for this trial, the PI should notify the administrative department for clinical trial of medical devices in the Clinical Investigation Site, and timely provide a detailed written explanation for discontinuation or suspension to the sponsor.

#### 7.9 Monitoring Plan

Monitoring is to verify that: I. Rights and health of the subject are protected; II. The reported data are accurate, intact and supported by the original document; III. This trial is implemented as per the protocol and conforms to applicable regulations and management procedures for the clinical trial.

Investigator's obligations during monitoring:

- (1) Provide completed CRF and relevant data and facilitate monitoring in terms of data traceability conditions, source materials and venues, etc.;
- (2) Coordinate relevant personnel to assist the monitoring.

Monitoring process:

- (1) Before monitoring, the monitor shall inform the investigator in advance, and notify the office of the Clinical Investigation Site if necessary;
- (2) The monitor shall confirm whether the problem found last time has been solved or not in each monitoring;
- (3) During monitoring, the monitor shall timely communicate with the investigator with regard to the problem found:
  - ◆ The monitor shall fill in the feedback form, and submit it to the investigator, if necessary, to the office of the Clinical Investigation Site;
  - ◆ The monitor shall supervise and urge the investigator to solve the found problem;

◆ After the completion of monitoring, the monitor shall prepare the monitoring and visiting report and submit it to the project leader.

Detailed rules and requirements of monitoring shall be subject to internal Standard Operating Procedures of the sponsor and in line with requirements of the administrative department for clinical trial in the Clinical Investigation Site, and comply with relevant national laws and regulations on clinical trials.

#### 8 TRIAL DURATION AND ITS JUSTIFICATION

#### 8.1 Trial Duration

This clinical trial will last about 5 months.

#### 8.2 Justification

Whether the localization is accurate or not can be determined by the CT examination. The localization needle will be removed together with the resected tissue upon resection of pulmonary nodules. Considering relevant literature and endpoint measurements of this trial, the screening and enrollment period is about 3 months. Taking ethical approval and statistical analysis into account, this clinical trial will last about 5 months.

#### **8.3 Enrollment Time**

Enrollment of all subjects is expected to take 3 months.

#### 8.4 Expected Duration of Each Subject

The expected duration of each subject is 1 week.

After admission, the investigator informs the patient of the trial, i.e., the informed consent process. The patient signs the ICF. The investigator screens the patient strictly as per inclusion & exclusion criteria of the protocol. The qualified patient will receive nodule resection surgery. Localization using the investigational medical device will be performed before surgery. Whether the localization is accurate or not can be determined by CT examination upon puncture (the endpoint measurement of effectiveness is the successful localization rate). The nodule resection surgery will be conducted immediately after localization. The localization needle will be removed together with the resected tissue in the surgery. Usability and safety of the device are also observed in the process. The duration is about 1 week.

#### 9 PROBABILITY ANALYSIS OF SUCCESS AND FAILURE

#### 9.1 Probability analysis of success

This clinical trial complies with relevant laws and regulations, including Good Clinical Practice and

Declaration of Helsinki, as well as requirements of the trial protocol. This protocol can be implemented only after having been approved by the ethics committee.

Signing the ICF before the trial guarantees the compliance of the subject. Objective indexes are used in the trial, endeavoring to avoid selection bias and information bias; the investigator strictly complies with inclusion criteria, to reduce any possible interference factor.

To sum up, this clinical trial is very likely to be successful.

#### 9.2 Probability Analysis of Failure

Failure of this trial may be caused by any problem of the investigational product, that the investigator fails to strictly execute the clinical protocol, operate and measure as per the specification, and that the drop-out/rejection rate is greater than 10 %, etc. However, these factors will be controlled within the acceptable range. Therefore, this clinical trial is very unlikely to be failing.

#### 10 PREDICTED SIDE EFFECTS AND COUNTERMEASURES

#### 10.1 Adverse Events

#### 10.1.1 Definition of adverse events

- An adverse event (AE) is any adverse medical event that occurred to a clinical investigation subject after receiving the investigational medical device and which does not necessarily have a causal relationship with this treatment.
- All AEs occurred during the trial must be faithfully recorded in the AE form. The investigator shall provide pointed treatment for the AE and follow up until the disappearance or stability of the symptom.

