#### Secondary objective

Evaluate and compare the adverse events probability, the localization time, and the pain degree of the novel localization device and hookwire.

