# 7.3 Investigational Product

Product name: Disposable pulmonary nodule localization needle

Manufacturer: Ningbo Senscure Biotechnology Co., Ltd.

Product specifications & model: SS510-10

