# 11 STATISTICAL METHODS

#### 11.1 Statistical Analysis Population

Full Analysis Set (FAS): Refer to the ideal subject set which is as close as possible to the intention-to-treat (ITT) principle. This dataset is obtained through rejecting the least subject from all enrolled subjects using a reasonable method.

Per-Protocol Set (PPS): also known as effective cases, effective samples and evaluable cases. Per-Protocol Set is a subset of subjects in the FAS whose compliance with the protocol is tight enough. The subjects are considered as compliant if they have received treatment, have measurements of primary indexes, and have no major protocol violation, etc.

Safety Analysis Set (SAS): The subject set used for safety and tolerance evaluation. The SAS shall include all subjects who have used this investigational medical device and have at least one safety record.

Here, we will use the FAS to analysis baseline information, and the primary endpoint and secondary endpoint will use the SAS to analysis.

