#### 11.3.4 Safety evaluation

The statistical description will be performed for the condition of each complication. A table will be made to describe the type, severity, frequency and relationship to the investigational medical device of the AE. The incidence rate of AE will be calculated. Study discontinuation due to AEs as well as severe or serious AEs

will be specially described. The statistical description will be performed for the working condition of the system.

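### As written, the Safety Analysis Set excludes the hookwire arm, yet it is the set named for the primary and secondary comparisons; the adverse event and causality wording has the same one-product fault

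*Protocol*

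**What the plan says.** All references are to the protocol.

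- **Product.** Section 7.3, on the investigational product, has a single entry: "Product name: Disposable pulmonary nodule localization needle", with "Product specifications & model: SS510-10". Hookwire is not listed there; 7.1 makes it the control.
- **Analysis set.** Section 11.1: "The SAS shall include all subjects who have used this investigational medical device and have at least one safety record". The same section uses the Full Analysis Set for baseline information and adds that "the primary endpoint and secondary endpoint will use the SAS to analysis".
- **Adverse events.** Section 10.1.1: "An adverse event (AE) is any adverse medical event that occurred to a clinical investigation subject after receiving the investigational medical device".
- **Causality.** Section 10.1.3 has two scales, one for relationship to the investigational device and one for relationship to surgery. The table planned in 11.3.4 reports "relationship to the investigational medical device of the AE".
- **Objectives and endpoints.** The primary objective (4.2) and primary endpoint (7.1) concern localization success with both devices. The secondary objective begins "Evaluate and compare the adverse events probability" and names both devices. The first secondary endpoint covers pneumothorax, hemorrhage and pleural reaction with each.

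**The concern.** The set that carries every endpoint comparison is defined by exposure to a product that only one arm is planned to receive. A statistician who applies 11.1 literally would have no control group for the primary test or for any secondary endpoint. The sentence would suit a single-arm device study; in a two-arm comparison it conflicts with the trial's purpose.

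The adverse event wording raises a related but smaller problem. If device relatedness is graded only against the novel needle, device-related events cannot be tabulated on the same footing in both arms, although comparing adverse events is a stated objective.

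Reinterpreting the text quietly at analysis is a poor answer. Section 11.8 requires strict adherence to the statistical plan and ethics committee approval for methods not specified in it, and 13.3 says the report will support device registration.

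**Working it through.** **The plan's own numbers.** Section 11.2 gives 116 control and 232 intervention patients before drop-out, and allows 15% drop-out.

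- Control: 116 / (1 − 0.15) = 136.5; stated 136.
- Intervention: 232 / (1 − 0.15) = 272.9; stated 273.
- Total: 136 + 273 = 409, as in 4.1 and 7.4.

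The rounding of 136.5 has no bearing on this point.

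**Step 1: who meets the SAS definition.** Membership needs use of the investigational device (11.1). That device is the novel needle alone (7.3), and control patients are localized with hookwire (7.1). A patient who received only hookwire does not qualify.

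**Step 2: how many are affected.**

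- Hookwire patients in the SAS as written: 0 of 136 planned.
- Share of planned enrollment excluded: 136 / 409 = 33%.
- Share on the numbers before drop-out: 116 / (116 + 232) = 116 / 348 = 33%.

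**Step 3: which analyses are affected.** Section 11.1 assigns both the primary and the secondary endpoints to the SAS. The hypothesis in 11.2 compares an assumed 97% success rate with an assumed 89% in the hookwire arm. With no hookwire patients in the set, that test cannot be computed, nor can the comparisons of complications, pain or procedure time.

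**Step 4: whether another set fills the gap.** The Full Analysis Set starts from all enrolled subjects and so covers both arms, but 11.1 gives it only the baseline description. The Per-Protocol Set is defined but assigned to no analysis. Section 11.7 rules out sensitivity analyses.

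**Step 5: adverse events and causality, side by side.**

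- Limited to the investigational device: the definition in 10.1.1, the first scale in 10.1.3, and the relationship column in 11.3.4.
- Not limited to it: 6.2 describes complications of the lung puncture with no mention of device; 7.1 names them as endpoints for hookwire; Table 1 schedules adverse event recording at all three visits without a split by arm.

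Collection in the hookwire arm is therefore intended. What no section supplies is a scale for relatedness to the hookwire: 6.2 does not deal with causality, and the second scale in 10.1.3 concerns surgery.

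**The case against.** The best defence is that the protocol uses the term loosely. Section 8.4 says, for the qualified patient and without regard to arm, that localization is done with the investigational device; taken strictly, that would give every randomized patient the novel needle. Section 4.1 describes hookwire by the same generic product name that 7.3 uses. Since 11.1 assigns two-device endpoints to the SAS, its authors must have meant users of either device. The causality criteria in 10.1.3 speak of a suspected product, which could be stretched to cover hookwire, and 11.3.4 first asks for a description of each complication without naming a device.

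As an account of intent, this stands. It does not repair the text: a term that means one product in 7.3 and apparently both devices in 8.4 should not decide who is analysed.

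The defence also limits what can be claimed. A reader might infer that the hookwire arm yields no adverse events under this plan. The documents do not support that: 6.2, 7.1 and Table 1 all cover hookwire patients, the second bullet of 10.1.1 requires all events during the trial to be recorded, and 10.2.2 covers any serious event whatever its relationship to the device. A reader might also infer biased ascertainment between arms. The protocol gives one visit schedule, one set of complication descriptions and one severity scale, with no collection method that differs by arm, so such bias is not shown. Nor does the text establish that the event window ought to open when the allocation envelope is opened; that would be a preference.

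**Conclusion.** The SAS rule in 11.1 is wrong as written and should be corrected. Followed literally, it removes all 136 planned hookwire patients (33% of 409) from the primary comparison and every secondary one, contrary to 4.2 and 7.1. The formal adverse event definition, the device-causality scale and the adverse event table share the one-product wording, and the practical gap there is that relatedness to the hookwire is not provided for.

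The 33% is the control arm's planned share, not an estimate of bias, and 136 is a planned minimum. The conclusion rests on taking 7.3 as defining the investigational device and on no control patient also having the novel needle used. The protocol's evident intent is to analyse both arms, so this is a contradiction within a stated rule and not evidence that the control group will in fact be dropped.

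**What to change.** 1. In 11.1, define the SAS as all subjects in whom either study localization device (novel device or hookwire) was used and who have one or more safety records.
2. In 10.1.1, 10.1.3(1) and 11.3.4, replace the reference to the investigational device with *study localization device (novel device or hookwire)*, so that causality is graded against the device used in each arm.
3. Reconcile the revised text with 6.2, 7.1 and Table 1, so that one description of adverse events applies to both arms.

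The cost is a wording amendment with the review that 13.4 requires. The case report form is not shown; it should be checked for a hookwire relatedness field, and one added if absent. The sample size is unaffected.
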